For the count endpoints (e.g., number of flares), negative binomial regression model will be used to assess treatment effect with treatment, visit, and stratification factors as covariates.

The Cox Proportional Hazards model will be used to assess the treatment effect for the time-to-event endpoint, i.e., time to flare.

Missing Data Imputation Definition

Censoring: For the time-to-event endpoint, i.e., time to flare, missing data will be considered as censored at the last available time for the information.

NRI-C: The NRI-C will categorize any subject who does not have an evaluation during a pre-specified visit window as a non-responder for the visit, except for missing data due to COVID-19 infection or logistical restriction, which will be handled by Multiple Imputation. In addition, subjects who prematurely discontinue from study drug will be considered as non-responders for all subsequent visits after discontinuation. Subjects will also be classified as non-responders as described in Section 5.4.

As Observed: As observed analysis will not impute values for missing evaluations, and thus a subject who does not have an evaluation on a scheduled visit will be excluded from the AO analysis for that visit. Regardless of premature discontinuation of study drug, all observed data will be used in the analysis. As observed analysis may be used for both categorical variables and continuous variables for sensitivity analysis.

Mixed-Effect Model Repeated Measurements: MMRM analysis will be conducted using a mixed-effect model for continuous variables. Data collected after study drug discontinuation or initiation of rescue treatment will not be included. The mixed model includes the categorical fixed effects of treatment, visit and treatment-by-visit interaction, main stratification factors, and the continuous fixed covariate of baseline measurement. An unstructured variance covariance matrix will be used. The parameter estimations are based on the assumption of data being missing at random and using the method of restricted maximum likelihood (REML).

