8.0 Efficacy Analyses

8.1 General Considerations

All efficacy analysis will be performed in the FAS.

AbbVie may terminate this study prematurely at any time, either in its entirety or partially (discontinue 1 or more treatment groups based on interim analysis), at any site. In the

event the study is partially terminated, efficacy analysis will be performed separately for the terminated treatment groups and for the continued treatment groups:

Terminated Treatment Groups

For terminated group(s), the descriptive statistics will be provided by treatment group for the following efficacy endpoints using observed case (OC) (defined in Section 8.3) through Week 48:

- Achievement of SRI-4 and steroid dose \leq 10 mg prednisone equivalent QD.
- Achievement of SRI-4.
- Achievement of BICLA.
- Number of mild, moderate, or severe flares per patient-year (respectively and overall) by SELENA SFI, assessed by number and types of flare per subject through Week 24 and Week 48.
- Steroid burden, assessed as change from Baseline.

The statistics include number of observations, mean, standard deviation, minimum, median, and maximum for continuous variables, and number and percentage of subjects for categorical variables.

Continued Treatment Groups

For continued treatment groups, the primary and secondary efficacy endpoints will be analyzed at the alpha level of 0.1 (two-sided). Multiplicity control is not planned for this study.

For all efficacy endpoints, the descriptive statistics will be provided by treatment group. The statistics include number of observations, mean, standard deviation, minimum, median, and maximum for continuous variables, and number and percentage of subjects for categorical variables.

Unless otherwise specified, any subject who is randomized based on a wrong stratum will be analyzed according to the actual stratum that the subject belongs to.

"Baseline" refers to the last non-missing observation before the first administration of study drug, or randomization if no study drug is given.

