8.2 Handling of Potential Intercurrent Events

Potential intercurrent events considered in this study include 1) premature discontinuation of the study drug; 2) initiation of rescue medications; 3) initiation or dose escalation of SLE-related corticosteroid. Intercurrent events will be handled using the following methods for the efficacy analysis:

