8.2.1 Premature Discontinuation of Study Drug

Data collected will be used regardless of premature discontinuation of the study drug.

8.2.2 Initiation of Rescue Medications or Initiation or Dose Escalation of SLE-Related Corticosteroid

Data collected on or after the occurrence of the rescue medications or initiation or dose escalation of SLE-related corticosteroid will be handled using the methods below for the efficacy analysis:

1. [REDACTED]
2. [REDACTED]
3. [REDACTED]

- 4. [REDACTED]
- 5. [REDACTED]
- 6. [REDACTED]

Intercurrent events above apply to all categorical endpoints. For continuous endpoints, data after intercurrent events above will be excluded from modeling (i.e., predicted from the model for analysis).

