MMRM analysis will be conducted using a mixed-effect model including observed measurements at all visits for continuous variables. Data collected on or after initiation of rescue treatment or after initiation or dose escalation of SLE-related corticosteroid as defined in [Section 8.2.2](#) will not be included. The mixed model includes the categorical fixed effects of treatment, visit and treatment-by-visit interaction, randomization stratification factors, and the continuous fixed covariate of baseline measurement. An unstructured variance covariance matrix will be used. The parameter estimations are based on the assumption of data being missing at random and using the method of restricted maximum likelihood (REML).

As Observed (AO)

AO analysis will not impute values for missing evaluations, and thus a subject who does not have an evaluation on a scheduled visit will be excluded from the AO analysis for that visit. Regardless of premature discontinuation of study drug or initiation of rescue treatment or initiation or dose escalation of SLE-related corticosteroid as defined in

Section 8.2.2, all observed data will be used in the analysis. As observed analysis may be used for both categorical variables and continuous variables for sensitivity analysis.

Multiple Imputation (MI)

As a sensitivity analysis, MI will be utilized for the primary endpoint. Data collected on or after the occurrence of intercurrent events defined in Section 8.2.2 will be considered as non-responder. When a subject is a responder at both before and after the visit window, the subject will be categorized as a responder for the visit. Otherwise, subjects who have no available measurements will be handled by multiple imputations. Details on MI can be found in NRI-C approach.

Observed Case (OC)

The OC analysis will not impute values for missing evaluations and, thus, a subject who does not have an evaluation on a scheduled visit will be excluded from OC analysis for that visit. In addition, the OC analysis will not use values on or after the occurrence of intercurrent events defined in Section 8.2.2.

Censoring

For the time-to-event endpoint, i.e., time to flare, missing data will be considered as censored at the last available time for the information.

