8.5.2 Main Analyses of Secondary Efficacy Endpoints

The attributes of the estimands corresponding to the secondary efficacy endpoints are summarized in [Table 2](#).

Table 2. Summary of the Estimand Attributes of the Secondary Efficacy Endpoints

Attributes of the Estimand					
Estimand Label	Treatment	Endpoint	Population	Handling of Intercurrent Events	Statistical Summary*
Binary Secondary Endpoint	• Elsubrutinib 60 mg QD and upadacitinib 30 mg QD	Achievement of SRI-4 at Week 24.	FAS	[REDACTED]	Difference in the percentage of subjects achieving each binary secondary endpoint between groups.
	• Elsubrutinib 60 mg QD and upadacitinib 15 mg QD	Achievement of BILAG-Based Combined Lupus Assessment (BICLA) response at Week 24.			
	• Elsubrutinib 60 mg QD and upadacitinib placebo QD	Achievement of Lupus Low Disease Activity State (LLDAS) at Week 24.			
	• Elsubrutinib placebo QD and upadacitinib 30 mg QD				
	• Elsubrutinib placebo QD and upadacitinib placebo QD				
Continuous Secondary Endpoint	• Elsubrutinib 60 mg QD and upadacitinib 30 mg QD	Steroid burden, assessed as change from Baseline at Week 24.	FAS	[REDACTED]	Difference in the mean change from Baseline in Continuous endpoint between groups.
	• Elsubrutinib 60 mg QD and upadacitinib 15 mg QD				
	• Elsubrutinib 60 mg QD and upadacitinib placebo QD				
	• Elsubrutinib placebo QD and upadacitinib 30 mg QD				
	• Elsubrutinib placebo QD and upadacitinib placebo QD				

Table 2. Summary of the Estimand Attributes of the Secondary Efficacy Endpoints (Continued)

Attributes of the Estimand					
Estimand Label	Treatment	Endpoint	Population	Handling of Intercurrent Events	Statistical Summary*
Count Secondary Endpoint	
 Elsubrutinib 60 mg QD and upadacitinib 30 mg QD Elsubrutinib 60 mg QD and upadacitinib 15 mg QD Elsubrutinib 60 mg QD and upadacitinib placebo QD Elsubrutinib placebo QD and upadacitinib 30 mg QD Elsubrutinib placebo QD and upadacitinib placebo QD 	Number of mild, moderate, or severe flares per patient-year (respectively and overall) by Safety of Estrogens in Lupus Erythematosus National Assessment (SELENA) SLEDAI Flare Index (SFI), assessed by number and types of flare (mild/moderate, severe, and any) per subject through Week 24 and through Week 48.	FAS	[REDACTED]	Ratio in the mean incidence rate of mild, moderate, or severe flares per patient-year between groups.

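### As visible, the main model for steroid burden excludes doses that follow a qualifying steroid increase, so it does not measure actual steroid use, and inconsistent wording leaves the direction of the distortion open

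*SAP*

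**What the plan says.** Steroid burden, as change from Baseline, is secondary endpoint 4 at Week 24 (SAP 3.2) and other endpoint 9 at all visits (SAP 3.3). It is the only entry in the continuous row of SAP Table 2, where the summary measure is "Difference in the mean change from Baseline in Continuous endpoint between groups". SAP 8.5.2 sends continuous endpoints with several post-Baseline visits to an MMRM, and SAP 8.6 carries the approach to the other endpoints.

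After study drug discontinuation, SAP 8.2.2 lists as further intercurrent events "initiation of rescue medications; 3) initiation or dose escalation of SLE-related corticosteroid". The handling of these events is stated in several places:

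- The lead-in to SAP 8.2.2 covers data on or after the event. Its six numbered items are redacted.
- The closing rule of SAP 8.2.2: "For continuous endpoints, data after intercurrent events above will be excluded from modeling (i.e., predicted from the model for analysis").
- The MMRM definition in SAP 8.3 leaves out "Data collected on or after initiation of rescue treatment or after initiation or dose escalation of SLE-related corticosteroid" and assumes missing at random.
- The Observed Case (OC) definition in SAP 8.3: "the OC analysis will not use values on or after the occurrence of intercurrent events".

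Terminated groups are summarised "using observed case (OC) (defined in Section 8.3) through Week 48". AO analyses, which keep every observed value, are planned for all secondary endpoints as additional analyses (SAP 8.3, 8.5.3).

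Protocol 7.3 says of the MMRM: "Data collected after study drug discontinuation or initiation of rescue treatment will not be included". SAP 8.2.1 differs on discontinuation: "Data collected will be used regardless of premature discontinuation of the study drug".

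**The concern.** For SLEDAI-2K or PhGA, setting aside values that follow extra steroid is a defensible way to separate the drug effect from the steroid effect. For steroid burden, the event set aside is a rise in the outcome itself. Reductions stay in the model, while values following a qualifying increase are replaced by predictions. The result is then not the change in steroid use that the endpoint's name promises.

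At stake are the between-arm difference and the arm means for a secondary endpoint tested at two-sided 0.1 (SAP 8.1), in a study meant to define doses for further development. Steroid burden was also among the endpoints specified for the interim analysis, with the SAP 8.5 methods (SAP 11.2.3).

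**Working it through.** **Reference figure.** The plan states no rate, SD or effect for steroid burden, so there is nothing to reproduce on this point. The only stated design figure, 78% to 91% power for the primary endpoint with 65 per arm, recomputes to 77.7% and 91.1% and has no bearing here.

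**Two readings.** The SAP 8.2.2 lead-in and the OC definition use *on or after*. The SAP 8.2.2 rule for continuous endpoints uses *after*. The MMRM definition uses *on or after* for rescue but *after* for steroid initiation or escalation. The readings differ when the raised dose is recorded at the event visit.

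**Assumed inputs.** Steroid burden is read as daily dose at Week 24. There are 65 per arm and six 4-weekly visits; 20% take no steroid at Baseline and the rest 5 to 20 mg. Background taper is 0.25 mg per visit (between-subject SD 0.15), visit noise SD 0.4 mg. Increases of 5 or 7.5 mg occur at Week 4 or 8, capped at 25 mg. Excluded values are predicted within arm by sequential regression on Baseline and earlier visits. There are 1,000 or 2,000 trials per scenario.

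**Reading 1, *on or after*.** Difference lost ≈ (gap in escalation rates) × (mean excess dose left at Week 24):

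- 20% v 10%, +5 mg held: 0.10 × 5 = 0.50 mg
- 30% v 15%, +5 mg held: 0.15 × 5 = 0.75 mg
- 30% v 15%, +7.5 mg held: 0.15 × 7.5 = 1.13 mg
- 30% v 15%, +7.5 mg, reduced 1.25 mg per visit: excess left is 7.5 - 5 × 1.25 = 1.25 mg (from Week 4) or 7.5 - 4 × 1.25 = 2.5 mg (from Week 8), mean 1.875 mg; 0.15 × 1.875 = 0.28 mg
- same, reduced 2.5 mg per visit: excess left is 0, so 0 mg

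Simulated active minus placebo (mg/day):

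| Placebo/active escalation | Increase | All recorded doses | *On or after* excluded |
|---|---|---|---|
| 20%/10% | +5, held | -0.49 | 0.01 |
| 30%/15% | +5, held | -0.73 | 0.01 |
| 30%/15% | +7.5, held | -1.14 | 0.00 |
| 15%/30% | +7.5, held | +1.12 | 0.00 |
| 30%/15% | +7.5, reduced 1.25 per visit | -0.28 | 0.01 |
| 20%/20% | +7.5, held | -0.02 | -0.01 |
| 30%/15%, active tapers 0.40 per visit | +5, held | -1.47 | -0.72 |

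With equal escalation the difference is intact, but the placebo mean moves from +0.30 to -1.19 mg (0.20 × 7.5 = 1.5). In the last row the part due to faster tapering survives: (0.40 - 0.25) × 6 visits × 80% on steroid = 0.72 mg.

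A second check fitted an unstructured MMRM (both arms taper 3 mg, escalators end 2.5 or 5 mg above Baseline, 40 replicates per scenario). With 25% v 15% escalating, -0.50 and -0.92 became 0.08 and -0.04. With 40% v 10%, -1.58 and -2.53 became 0.09 and 0.03.

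**Reading 2, *after* only, raised dose recorded at the event visit.** Inputs: 30%/15%, +7.5 mg held. All recorded doses give about -1.1 mg. The SAP method gives about -1.2 to -1.3 mg at taper SD 0.15 and about -3.7 to -3.9 mg at SD 0.7. The raised value stays in the model and is projected forward; with a wide spread of tapering rates the model treats the jump as a trend. A later reduction would not correct this, because the visits that show it are the ones excluded.

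**The case against.** The strongest objection is redaction. The six items of SAP 8.2.2 and the intercurrent-event cells in Table 2 and Appendix D are blacked out. Steroid burden is alone in its row, so an exemption could sit in that cell. The items may also narrow which increases qualify; protocol 5.4 lists rescue steroid increases only through Week 8. This stands, and it keeps the point conditional.

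Second, SAP 2.1 declares a hypothetical estimand for continuous secondary endpoints, so this could be called a matter of preference. That stands in part. Section 2.1 names only rescue medications, whereas SAP 8.2 lists steroid initiation or escalation as a separate event.

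Third, much is already covered. AO keeps all doses, and without a testing hierarchy its label costs no alpha. The primary endpoint (at most 10 mg) and LLDAS (at most 7.5 mg) carry dose limits, the same events count as non-response under NRI-C, and other endpoints 26 and 27 count subjects at or below 7.5 mg. This stands and limits the seriousness. But AO is not the main analysis, and terminated groups are specified with OC summaries only.

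A reader might infer that the main analysis always shows tapering as if no extra steroid had been taken, and so always loses the escalation difference. The documents do not support that: it follows only under the *on or after* reading.

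**Conclusion.** On the visible text, the main MMRM of steroid burden does not measure actual steroid use. Under *on or after*, it approximates tapering without a qualifying increase, and a difference due to lasting escalation is lost, whichever arm escalates more. For a gap of 10 to 15 points and 0 to 7.5 mg of excess remaining, the loss is 0 to 1.1 mg/day; increases tapered off before Week 24 cause little distortion. Under *after*, with the raised dose recorded at the event visit, the difference is kept or exaggerated. If the increase begins between visits, so that the first raised value is recorded later, the first result applies.

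These sizes rest on assumed rates, durations and a daily-dose reading of an endpoint that the SAP does not define further. The real size is unknown. It would also be wrong to infer that the rule favours the active arms, or that actual use goes unreported: the direction depends on the wording and on which arm escalates more, and AO reports all doses. The primary analysis is unaffected. The point is worth fixing, subject to the redacted text.

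**What to change.** Unless a redacted item already does so:

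1. Exempt steroid-dose endpoints (secondary 4, other 9) from the SAP 8.2.2 exclusion.
2. Make the analysis of all recorded prednisone-equivalent doses, as in the planned AO analysis, the main one.
3. Keep the current MMRM as supplementary, with one consistent choice between *on or after* and *after* in SAP 8.2.2 and 8.3.
4. Align SAP 2.1, Table 2, Appendix D and the OC summary of steroid burden for terminated groups.
5. Give protocol 7.3 the same exemption, or record the departure in the SAP, and reconcile its exclusion of data after study drug discontinuation with SAP 8.2.1.

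The cost is wording. No new data are needed: protocol Appendix D has steroid therapy assessed at every visit, and AO analyses are already planned. The downside is that the main result then includes rescue steroid, usually has a larger standard error, and uses a different estimand from the other continuous endpoints.

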8.3 Handling of Missing Data

Missing data could occur due to various reasons, including missing visits/assessments, early withdrawal from the study, or missing due to Coronavirus disease 2019 (COVID-19) infection or logistic restriction.

The COVID-19 pandemic is interfering with the conduct of many ongoing trials, with potential impacts on treatment duration and the collection, analysis and the interpretation of clinical trial data. Some protocol-specified visits in the clinical trials may be impacted due to COVID-19 infection or logistical restrictions during the pandemic. For example, some scheduled visits may be missed due to self-quarantine or local government restrictions on travel; some visits may also be delayed or canceled due to healthcare resource constraints during the pandemic. Impacted visits due to COVID-19 will be recorded in the database. The probability of having missed visits and missing data due to COVID-19 infection or logistical restrictions related to the COVID-19 pandemic can be reasonably assumed to be unrelated to the unobserved values. Therefore, for the purpose of statistical analysis, it is reasonable to assume that these missing data are missing at random (MAR) and the statistical models that require MAR assumption are appropriate. The intent is to provide reliable estimates of the treatment effects targeted in the protocol

under the scenario without the impact of COVID-19 pandemic. Number of subjects with missing values due to COVID-19 will be presented.

Missing data and intercurrent events will be handled using the following methods for the efficacy analysis.

Non-Responder Imputation (NRI) incorporating Multiple Imputation (MI) to handle missing data due to COVID-19 (NRI-C)

- The NRI-C will categorize any subject who does not have an evaluation during a pre-specified visit window (either due to missing assessment or due to early withdrawal from the study) as a non-responder for the visit. There are two exceptions which will be handled in the order below:
 - 1) when a subject is a responder at both before and after the visit window, the subject will be categorized as a responder for the visit.
 - 2) missing data due to COVID-19 infection or logistical restriction and not satisfying 1) will be handled by MI.

Of note, subjects will be counted as non-responders, thereafter, and will not be imputed using 1) or 2), on or after the intercurrent event as specified in Section [8.2.2](#).

- Details on MI method are described below:

MI will be performed using observed data excluding data on or after intercurrent events specified in Section [8.2.2](#). Markov Chain Monte Carlo (MCMC) will be first applied to augment data into monotonic missing pattern, where applicable, and PROC MI will be used to generate 30 datasets using the regression method. If the binary endpoints are derived from the continuous variables, PROC MI will be applied to the continuous variables. The variables to be included in the imputation model are: treatment group, randomization stratification factors (baseline corticosteroid dose above 10 mg prednisone-equivalent (≤ 10 mg or > 10 mg), screening SLEDAI-2K (< 10 or ≥ 10), baseline interferon score (high or low or not applicable), baseline immunosuppressant (yes or no), gender, pooled race (White, Black, Asian, or Other), ethnicity, pooled geographic region (North America/South America,

Europe, or Asian), age, baseline BMI, and if applicable, baseline measurement and post-baseline measurements at each visit up to the end of the analysis period. The random seed for MCMC and the random seed for PROC MI are specified in [Appendix E](#). The imputed post-baseline measurements will be rounded to the same precision as the observed data before the determination of responder status. Prior to applying CMH model, subjects will be characterized as responders or non-responders based on MI imputed values if missing due to Covid-19, otherwise subjects will be considered as non-responder for missing due to other reasons in the NRI-C approach. Using the CMH model adjusted by randomization stratification factors, the endpoints will be analyzed using each of the 30 imputed datasets. SAS PROC MIANALYZE will be used to generate the final inferences of the risk difference using Rubin's rule. The rules of handling intercurrent events, as specified in [Section 8.2.2](#), will be applied before and after applying MI for efficacy assessments.

Mixed-Effect Model Repeated Measurements (MMRM)

MMRM analysis will be conducted using a mixed-effect model including observed measurements at all visits for continuous variables. Data collected on or after initiation of rescue treatment or after initiation or dose escalation of SLE-related corticosteroid as defined in [Section 8.2.2](#) will not be included. The mixed model includes the categorical fixed effects of treatment, visit and treatment-by-visit interaction, randomization stratification factors, and the continuous fixed covariate of baseline measurement. An unstructured variance covariance matrix will be used. The parameter estimations are based on the assumption of data being missing at random and using the method of restricted maximum likelihood (REML).

As Observed (AO)

AO analysis will not impute values for missing evaluations, and thus a subject who does not have an evaluation on a scheduled visit will be excluded from the AO analysis for that visit. Regardless of premature discontinuation of study drug or initiation of rescue treatment or initiation or dose escalation of SLE-related corticosteroid as defined in

Section 8.2.2, all observed data will be used in the analysis. As observed analysis may be used for both categorical variables and continuous variables for sensitivity analysis.

Multiple Imputation (MI)

As a sensitivity analysis, MI will be utilized for the primary endpoint. Data collected on or after the occurrence of intercurrent events defined in Section 8.2.2 will be considered as non-responder. When a subject is a responder at both before and after the visit window, the subject will be categorized as a responder for the visit. Otherwise, subjects who have no available measurements will be handled by multiple imputations. Details on MI can be found in NRI-C approach.

Observed Case (OC)

The OC analysis will not impute values for missing evaluations and, thus, a subject who does not have an evaluation on a scheduled visit will be excluded from OC analysis for that visit. In addition, the OC analysis will not use values on or after the occurrence of intercurrent events defined in Section 8.2.2.

Censoring

For the time-to-event endpoint, i.e., time to flare, missing data will be considered as censored at the last available time for the information.

